Setting/Participants: Eligible patients >6 months and <18 years with clinician concern for septic shock who require at least 20 ml/kg of fluid resuscitation will be enrolled in the Emergency Department of the Children’s Hospital of Philadelphia. Patients will be enrolled prior to receipt of >40 mL/kg IV/IO crystalloid fluid. Due to the life-threatening nature of septic shock and the narrow therapeutic window for fluid resuscitation, potential subjects will be enrolled through the federal “exception from informed consent” (EFIC) process, with prospective informed consent obtained as possible in rare circumstances.

Study Interventions and Measures: Seventy subjects will be randomized to receive either open-label NS or LR for all remaining fluid administration (bolus and maintenance) until 11:59pm on the calendar day following randomization such that all patients receive at least 24 hours of study fluid. The primary feasibility outcome for this pilot study will be the proportion of total crystalloids administered as the correct study fluid within each randomized arm (Aim 1). Secondary outcomes will include mean proportion of total crystalloids administered as non-study fluid in each arm (Aim 1), percent enrollment/randomization/treatment of eligible patients (Aim 2), and successful EFIC approval with <10% subject withdrawal. Specified safety outcomes will be monitored as they occur in the course of routine clinical practice but this pilot study will not be powered to assess safety given that both fluids are FDA-approved and have well-described efficacy and safety profiles.

PROTOCOL SYNOPSIS

Study Title	Feasibility Study for the Randomized Pragmatic Pediatric Trial of Balanced versus Normal Saline Fluid in Sepsis (PRoMPT BOLUS – Feasibility)
Funder	The Children's Hospital of Philadelphia
Clinical Phase	Pilot/feasibility study

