Efficacy Evaluations	Feasibility will be assessed as part of each aim as follows: 
 • Aim 1: proportion of total crystalloids administered as saline in each arm (primary) and proportion of total crystalloids administered as non-study fluid (i.e., cross-over) in each arm (secondary) • Aim 2: percent enrollment/randomization/treatment of eligible patients • Aim 3: successful EFIC approval with $\leq 10\%$ subject withdrawal Efficacy outcomes, including mortality, hospital-free days, dialysis, and length of stay, will be collected in preparation for a subsequent multicenter trial, though this pilot feasibility study will not be powered to analyze these endpoints.
Safety Evaluations	For this single-site feasibility study, specified safety outcomes will be monitored as they occur in the course of routine clinical practice but this feasibility study will not be powered to assess safety given that both fluids are FDA-approved and have well-described efficacy and safety profiles.
Statistical And Analytic Plan	The statistical plan will be descriptive for this feasibility study.

For Aim 1, feasibility will be defined by either:

- 1) an absolute difference in the mean use of NS between study arms of at least 65% with a lower 95% CI border of >60%,
or
- 2) at least 85% of subjects in the NS arm receiving $\geq 90\%$ of study fluid as NS during the study window *and* at least 80% of subjects in the LR arm receiving $\geq 75\%$ of study fluid as LR.

The secondary endpoints will be defined as meeting feasibility criteria if:

- The proportion of eligible patients treated in the pediatric ED who are enrolled, randomized, and treated with study fluid is $>65\%$.
- EFIC is approved by the IRB at CHOP
- The proportion of eligible patients who meet criteria for EFIC who are not enrolled or who are enrolled but withdraw prior to completion of the follow-up phase is $\leq 10\%$.

Data and Safety Monitoring Plan

Data will be managed and stored by the University of Utah Data Coordinating Center. In addition the PI, an independent Data Safety Monitoring Board (DSMB) will be convened to ensure data quality and patient safety.

[figure not shown]
TABLE 1: SCHEDULE OF STUDY PROCEDURES

Study Phase	Screening	Intervention		Follow-Up¹
Study Day	1	1	2	2 to 90²
Informed Consent/Assent or EFIC	X			
Review Inclusion/Exclusion Criteria	X	X	X	X
Inform patient/LAR of study enrolment (if EFIC)		X	X	X
Demographics/Medical History	X			X

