The outcomes for Aim 3 will be the proportion of eligible patients who meet criteria for EFIC who are not enrolled, randomized, and treated with study fluid or, if enrolled, withdraw prior to completion of the follow-up phase. This outcome will be measured by dividing the number of patients eligible but not enrolled through EFIC and/or withdraw prior to completion of the follow-up phase (numerator) by the number of eligible patients who meet criteria for EFIC (denominator) over the entire enrollment period of the study.

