6.2 Secondary Endpoints

Secondary endpoints will include the following:

- The proportion of total crystalloids administered as non-study fluid (i.e., cross-over) in each arm (Aim 1).
- The proportion of eligible patients treated in the pediatric ED who are enrolled, randomized, and treated with study fluid (Aim 2).
- The proportion of eligible patients who meet criteria for EFIC who are enrolled, randomized, and treated with study fluid *and* do not withdraw prior to completion of the follow-up phase.

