6.3.2 Feasibility Analysis

The primary analysis will be based on an intention-to-treat approach and will include all subjects randomized whether or not study fluid was administered.

The primary endpoint will be defined as meeting feasibility criteria if either of the following criteria are met:

- 3) There is an absolute difference in the mean use of NS between arms of at least 65% with a lower 95% CI border of >60%. For example, feasibility criteria would be met if 90% of crystalloid fluid in the NS arm was NS compared to only 25% in the LR arm. The proportion of NS use in each arm will be compared using the chi-squared test with a 95% bootstrap confidence interval with bias correction (assuming skewed distribution of data) around the difference in the proportion of NS use in each arm.
- 4) At least 85% of subjects in the NS arm receive $\geq 90\%$ of study fluid as NS during the study window *and* at least 80% of subjects in the LR arm receive $\geq 75\%$ of study fluid as LR.

The secondary endpoints will be defined as meeting feasibility criteria if:

- The mean proportion of total crystalloids administered as non-study fluid (i.e., cross-over) is $\leq 25\%$ in each arm (for example, $\leq 25\%$ of total crystalloid is administered as NS for patients randomized to the LR arm).
- The proportion of eligible patients treated in the pediatric ED who are enrolled, randomized, and treated with study fluid is $>65\%$.
- EFIC is approved by the IRB at CHOP
- The proportion of eligible patients who meet criteria for EFIC who are not enrolled or who are enrolled but withdraw prior to completion of the follow-up phase is $\leq 10\%$.

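### The Aim 3 limit of 10% is applied to withdrawal alone in two summary lines but to non-enrolment or withdrawal in the analysis section, and the definitions differ on whether treatment is required

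*Combined protocol and SAP*

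**What the plan says.** The Aim 3 criterion is stated in six places, which fall into three groups.

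- **Withdrawal only, with a 10% limit.** The abstract asks for "successful EFIC approval with <10% subject withdrawal". The Efficacy Evaluations row of the synopsis reads "Aim 3: successful EFIC approval with" and continues with at most 10% subject withdrawal. Neither gives a denominator.
- **Not enrolled or withdrawn, with a 10% limit.** The synopsis statistical plan limits to at most 10% the proportion of eligible patients "who meet criteria for EFIC who are not enrolled or who are enrolled but withdraw prior to completion" of follow-up. Section 6.3.2 repeats this for patients "who are not enrolled or who are enrolled but withdraw prior to completion of the follow-up phase". The measurement sentence of Section 5.2.3 agrees in substance: its numerator is "the number of patients eligible but not enrolled through EFIC and/or withdraw prior to completion of the follow-up phase (numerator", over eligible patients who meet EFIC criteria.
- **Treatment also required, with no limit stated.** The first sentence of Section 5.2.3 counts patients "who are not enrolled, randomized, and treated with study fluid or, if enrolled, withdraw prior to completion of the follow-up phase". Section 6.2 gives the complement, as the proportion "who meet criteria for EFIC who are enrolled, randomized, and treated with study fluid" and not withdrawing.

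Aim 2 (Section 6.3.2) requires that more than 65% of eligible ED patients be enrolled, randomized and treated.

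**The concern.** Withdrawal alone measures retention after enrolment. The 6.3.2 quantity also counts every EFIC-eligible patient who was never enrolled, for whatever reason. A pilot can do well on the first and badly on the second, so a reader of the abstract and a reader of Section 6.3.2 would expect different results to count as success.

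This matters because Section 1.1 presents these criteria as the evidence that the larger multicenter trial can succeed. The synopsis rationale lists effectiveness of enrolment and acceptability of EFIC as separate assessments, yet neither version of the criterion isolates acceptability. Under 6.3.2, patients missed for logistical reasons count against EFIC even if no family objected. Under withdrawal-only, a family that objects at the bedside is not enrolled (Section 9.6.3) and so never appears as a withdrawal.

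**Working it through.** The plan gives no sample size, power or precision for Aim 3, so there is no stated figure to reproduce. The check is a comparison of the definitions followed by direct arithmetic.

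**Inputs from the documents**
- Enrolled, n: 70, where recruitment stops (Section 3.3.2). The synopsis gives 80 subjects, and Section 3.3.2 also expects about 80 enrolled to yield 70 evaluable, so both values are used.
- Limits: at most 10% for Aim 3 and more than 65% for Aim 2 (Section 6.3.2).

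**Assumptions for illustration**
- All E eligible patients meet EFIC criteria. Inclusion criterion 6 makes EFIC the route when time does not permit consent, and Section 9.6.1 calls prospective consent rare.
- All enrolled subjects are treated and none withdraws (w = 0).
- Withdrawal-only uses enrolled subjects as its denominator, since the documents give none.

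**Formulas**
- Withdrawal-only = w/n
- Section 6.3.2 = (E − n + w)/E
- Aim 2 = n/E when all enrolled are treated

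With w = 0, the 6.3.2 limit (E − n)/E ≤ 0.10 is the same as n/E ≥ 0.90. Under these assumptions Aim 3 therefore requires 90% enrolment.

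**Results**

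| n | E | Section 6.3.2 | Withdrawal-only | Aim 2 |
|---|---|---|---|---|
| 70 | 77 | 7/77 = 9.1%, pass | 0%, pass | 70/77 = 90.9%, pass |
| 70 | 78 | 8/78 = 10.3%, fail | 0%, pass | 70/78 = 89.7%, pass |
| 70 | 107 | 37/107 = 34.6%, fail | 0%, pass | 70/107 = 65.4%, pass |
| 70 | 108 | 38/108 = 35.2%, fail | 0%, pass | 70/108 = 64.8%, fail |
| 80 | 88 | 8/88 = 9.1%, pass | 0%, pass | 80/88 = 90.9%, pass |
| 80 | 89 | 9/89 = 10.1%, fail | 0%, pass | 80/89 = 89.9%, pass |
| 80 | 123 | 43/123 = 35.0%, fail | 0%, pass | 80/123 = 65.04%, pass |
| 80 | 124 | 44/124 = 35.5%, fail | 0%, pass | 80/124 = 64.5%, fail |

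The two Aim 3 quantities disagree for 78 to 107 eligible with n = 70, and for 89 to 123 with n = 80. That is most of the range in which Aim 2 succeeds.

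**Sensitivity (n = 70).** If up to 7 of the 70 were enrolled by prospective consent and so leave the EFIC denominator, the lower end stays at 78: with 7, 77 eligible gives 7/70 = 10.0% (pass) and 78 gives 8/71 = 11.3% (fail). If r missed patients had declined prospective consent, the lower end becomes 78 + r, for example 83 when r = 5.

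**Inequality.** Strict and non-strict limits differ only at an exact tie, such as 7/70 = 10.0%.

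**Treatment element.** With u subjects enrolled but untreated, the first sentence of 5.2.3 gives (E − n + w + u)/E. The documents give no value for u. Purely as an example, 74 eligible, 70 enrolled, 65 treated and none withdrawn gives 4/74 = 5.4% under 6.3.2 and 9/74 = 12.2% when the untreated count. The second figure breaches 10% only if the 6.3.2 limit is carried over to a sentence that states no limit.

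**The case against.** The strongest reply is that the operative rule is consistent. Section 6.3.2, the synopsis statistical plan and the 5.2.3 measurement sentence agree in substance; the outliers are two summary lines without a denominator. This largely stands. A reader might infer that the plan leaves Aim 3 free to pass or fail according to which section is followed. The documents do not support that, because an analyst would have to prefer abstract shorthand to the statistical section. What remains is that two summary lines state a different success criterion from the one to be applied.

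A reader might also infer that the treatment discrepancy will change the result. That is not shown. Neither the first sentence of 5.2.3 nor 6.2 carries a limit. The statement that the analysis "will include all subjects randomized whether or not study fluid was administered" concerns the primary analysis. Inclusion criterion 5 requires that more fluid be thought likely to be needed, so untreated subjects may be few. The definitions still disagree, but by an unknown amount.

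Nor is it supported that investigator-initiated or pregnancy withdrawals are left undefined. Section 3.1.3 classifies each subject as completing or withdrawing, Section 4.6 puts subject and investigator withdrawal under one heading, and the Aim 3 wording does not restrict by cause. The natural reading is that all count.

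Finally, counting missed patients fits the objective in Section 2.2, which is feasibility of enrolment using EFIC, and reasons for non-enrolment are already collected (Section 4.1). Both points are fair. The composite is a legitimate choice, but the plan does not say that its components will be reported separately.

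**Conclusion.** The inconsistency is real and worth correcting, at the level of a secondary feasibility criterion; Aim 1 is unaffected. The 10% limit describes withdrawal in the abstract and the synopsis evaluations row, and non-enrolment or withdrawal in the synopsis statistical plan and Section 6.3.2. If nearly all eligible patients meet EFIC criteria, as the protocol expects, the 6.3.2 version requires about 90% enrolment even with no withdrawals, against more than 65% for Aim 2. The bands of 78 to 107 eligible (70 enrolled) and 89 to 123 (80 enrolled) depend on the stated assumptions of full treatment, no withdrawal and universal EFIC eligibility. The lower end is not sensitive to a few prospective consents.

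The treatment discrepancy is secondary and its size cannot be determined from the documents. The change of direction between 5.2.3 and 6.2 is not in itself an error, since one is the complement of the other.

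**What to change.** Before data review:

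1. Use one Aim 3 numerator, denominator and inequality throughout, with Section 6.3.2 as the base, and align the abstract and the synopsis evaluations row to it.
2. Make Sections 5.2.3, 6.2 and 6.3.2 agree on whether subjects enrolled but not treated count as failures.
3. Have the sponsor confirm that 10% is the intended limit for the chosen definition, given that it implies about 90% enrolment.
4. Report the components separately: (a) objection or opt-out plus withdrawal by the subject or LAR, and (b) non-enrolment for other reasons. Missed enrolment would then not be read as EFIC being unacceptable.

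The data for item 4 are already planned: reasons for non-enrolment under Section 4.1, and documented LAR decisions under Section 9.6.3. The cost is wording changes and one extra table, with no new procedures.

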5.3 Efficacy Evaluation

This pilot study will not be powered to determine efficacy. However, the following efficacy outcomes planned for use in a subsequent large pragmatic trial will be measured:

- All-cause hospital mortality (censored at 90 days following randomization), measured as vital status at hospital discharge
- Hospital-free days, measured as the number of calendar days alive and out of the hospital between randomization (day 0) and day 27. Patients who die prior to hospital discharge will be recorded as “zero” hospital-free days. Because follow-up will not proceed after hospital discharge, patients who may have died after hospital discharge but before day 27 will be recorded as having as many hospital-free days up to day 27 as if they had survived to day 27.
- New inpatient dialysis, measured as treatment (or intention to treat if subject does not tolerate treatment) with any renal replacement therapy (including slow continuous ultrafiltration, continuous or intermittent hemodialysis, hemofiltration, or hemodiafiltration, or peritoneal dialysis) that was not a continuation of pre-hospital chronic therapy.
- Hospital length of stay, measured as the number of calendar days between ED arrival and ED or hospital discharge (whichever occurs later).

5.4 Safety Evaluation

This pilot study will not be powered to determine safety. However, the following safety outcomes planned for use in a subsequent large pragmatic trial will be measured if ascertained as part of routine clinical practice:

- Hyperlactatemia, measured as at least one venous or arterial blood lactate measurement >4 mmol/L within four calendar days of randomization
- Hyperkalemia, measured as at least one venous or arterial blood potassium measurement >6 mEq/L (without hemolysis) within four calendar days of randomization
- Hypercalcemia, measured as at least one venous or arterial blood ionized calcium measurement of >1.35 mEq/L or total calcium >12 mEq/L within four calendar days of randomization

- Hypernatremia, measured as at least one venous, arterial, or capillary blood sodium measurement of >155 mEq/L within four calendar days of randomization
- Hyponatremia, measured as at least one venous, arterial, or capillary blood sodium measurement of <128 mEq/L within four calendar days of randomization
- Hyperchloremia, measured as at least one venous, arterial, or capillary blood chloride measurement of >110 mEq/L within four calendar days of randomization
- Clotting of intravenous line in patients who received both ceftriaxone and LR, within four calendar days of randomization
- Therapy for brain herniation, measured as treatment with hyperosmolar therapy (hypertonic saline and/or mannitol) for radiographic and clinical determination of new impending or present brain herniation (but not including a presumptive clinical diagnosis of brain herniation that is disproven by subsequent radiographic studies) within four calendar days of randomization
- Therapy for thromboembolism, measured as radiographic or clinical determination of new venous or arterial thromboembolism requiring initiation of therapeutic anticoagulation for the purposes of treating thromboembolism, within seven calendar days of randomization

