3.2 Allocation to Treatment Groups and Blinding

Randomization will be performed using 1:1 permuted blocks. Randomization sequence will be generated prior to the start of the study and will be filed using a series of numbered, opaque envelopes. Envelopes with study arm assignment will be stored in close proximity to crystalloid fluids in the CHOP ED. Treatment allocation will be revealed to the clinical care team after eligibility for enrollment has been determined to be appropriate by asking a member of the care team to open the next sequentially numbered envelope. The number of the envelope and study arm assignment will be recorded in a log after opening the envelope. The clinical team will then be directed to use the assigned study fluid for all subsequent crystalloid fluid administration within the remainder of the study window. Compliance with study fluid administration will be the primary feasibility assessment in this study (Aim 1).

Fluid administration will be open-label and neither the subject nor the care team will be blinded to the allocated treatment assignment. Blinding study fluid is not pragmatic and unlikely to even be possible. In the SPLIT fluid trial, two-thirds of clinicians correctly identified the randomized crystalloid patients received as electrolyte differences following NS or LR provide clear indication of fluid selection.³⁵ However, randomization following study enrollment will help to minimize selection bias that might occur due to pre-enrollment awareness of study group assignment.

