4.6.1 Early Termination Point

Subjects who withdraw from the study will have all procedures enumerated for the follow-up phase in Section 4.3 performed at the early termination point (rather than at hospital discharge or study day 90).

In addition, subjects randomized to LR in this unblinded study for whom routine, clinician-directed physical and/or laboratory assessment reveals the following criteria within the up-

to-48 hour time window of the intervention phase will not be required to receive additional study fluid as part of this protocol and will be transitioned to an appropriate fluid as determined by the discretion of the treating clinical team. Recognizing that hepatic and renal injury are a) common in septic shock, b) often improved by fluid resuscitation, and c) vary along a spectrum of mild dysfunction (common) to severe failure (uncommon), stopping criteria are defined when either an immediate unsafe condition is noted or when persistent or worsening organ injury indicates that continued LR administration may be cumulatively unsafe (e.g., potassium administration despite worsening oliguria or lactate administration despite worsening hepatic function).

- Hyperkalemia defined as blood potassium >6 mEq/L confirmed on immediate repeat testing
- Hypercalcemia defined as blood total calcium >12 mg/dL or ionized calcium >0.35 mmol/L confirmed on immediate repeat testing
- Severe hepatic impairment defined as rise in blood ALT to $>10,000$ U/L or total bilirubin >12.0 mg/dL
- Severe renal impairment defined as initiation of renal replacement therapy (continuous or intermittent hemodialysis or peritoneal dialysis) or urine output <0.5 ml/kg/hr for 16 hours

NOTE: Hepatic impairment was defined as a fulminant rise in ALT or total bilirubin because other markers of liver function are not commonly recommended for use in pediatric septic shock. For example, an acute elevation in INR is more commonly indicative of hematologic dysfunction than hepatic impairment in pediatric septic shock.⁵⁰

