NOTE: Urine output <0.5 ml/kg/hr for 16 hours indicates renal injury (“I”) in the pRIFLE scoring system and stage II kidney injury in the KDIGO scoring system.⁵¹ Creatinine and creatinine clearance will not be used as stopping criteria in the absence of oliguria or initiation of renal replacement therapy because intermittent lab testing may limit the utility of these measurements compared to continuous urine output monitoring and blood creatinine is a poor proxy for a patient’s handling of potassium in that most acute kidney injury in sepsis is caused by acute tubular necrosis, which promotes electrolyte wasting despite a rise in blood creatinine. As an example, in a prior randomized trial of NS versus LR following kidney transplant (as a model of severe acute kidney injury), 19% of patients in the NS developed hyperkalemia >6 mEq/L compared to 0% in the LR group.⁵² Consequently, urine output is the most useful clinical indicator of potential electrolyte retention.

The laboratory values noted above, including potassium, total calcium, ionized calcium, ALT, and bilirubin, will be ordered as determined to be clinically indicated by the treating clinical team rather than prescribed by this study protocol. Because patients with septic shock have wide variability in illness severity and clinical course, including large differences in the amount and timing of fluid administration, pre-specifying which laboratory values to obtain and when to obtain them could result in additional unnecessary phlebotomy and/or access of indwelling lines both of which would impose additional harm (e.g., pain) and risk (e.g., central-line associated bloodstream infection risk increases with additional line accesses) that may not have been experienced outside of the study. Therefore, rather than pre-specifying in the study protocol the laboratory values to obtain

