6.3.4 Safety Analysis

Safety endpoints will be tracked between groups as part of this pilot study, but no formal statistical comparisons will be undertaken due to insufficient statistical power. As part of our secondary feasibility analysis, however, we will determine the proportion of patients with complete data available for each safety endpoint listed in Section 5.5 to ensure that it is indeed feasible to capture the safety outcome measures planned for a subsequent large multicenter trial. Specifically, we will track laboratory testing performed as part of routine clinical practice in order to determine the frequency that laboratory results are available for the specified safety outcome measures listed in Section 5.4. It is notable that routine clinical practice for sepsis includes frequent (i.e., daily or more) measurement of blood lactate, sodium, potassium, chloride, and calcium.

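### The laboratory safety outcomes in 5.4 depend on how often unblinded clinicians test, and 6.3.4 does not commit to reporting testing by arm

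*Combined protocol and SAP*

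**What the plan says.** Section 5.4 introduces its list by saying that "the following safety outcomes planned for use in a subsequent large pragmatic trial will be measured if ascertained as part of routine clinical practice". Six entries are laboratory outcomes: high lactate, potassium, calcium, sodium and chloride, and low sodium. All have the same form. Hyperkalemia, for example, is "measured as at least one venous or arterial blood potassium measurement >6 mEq/L (without hemolysis) within four calendar days of randomization".

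On who decides to test, section 4.6.1 says that the values used in its stopping criteria "will be ordered as determined to be clinically indicated by the treating clinical team rather than prescribed by this study protocol", and 5.1.2 requires no laboratory test for the study. Section 3.2 says that "neither the subject nor the care team will be blinded to the allocated treatment assignment".

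The laboratory and organ-function stopping criteria in 4.6.1 concern "subjects randomized to LR in this unblinded study for whom routine, clinician-directed physical and/or laboratory assessment reveals the following criteria". They include potassium and calcium limits, each to be confirmed by an immediate repeat. The hypersensitivity stop in the same section covers both arms.

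On analysis, section 6.3.4 says: "Safety endpoints will be tracked between groups as part of this pilot study". It rules out formal comparisons. It also commits to determining the proportion of patients with complete data for each safety endpoint and how often laboratory results are available. It does not say whether availability will be split by arm, whether tests per subject will be counted, or what denominator the event rates will use.

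**The concern.** With an any-abnormal-value definition, every extra test is another chance to become an event. That does no harm to a comparison if both arms are tested equally. Here there is no fixed schedule and the person ordering the test knows the fluid. For two of the analytes, potassium and calcium, the protocol also attaches a stopping rule to one arm only, which gives clinicians an arm-specific reason to look.

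If testing differed, the by-arm table would mix testing intensity with fluid effect, in whichever direction the testing ran. Section 5.4 says that these outcomes are intended for the larger trial, and 6.3.4 says that the pilot should show whether they can be captured. Whether capture is comparable between arms is part of that question, and the plan does not undertake to answer it.

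**Working it through.** The documents give no event rate, test count or power for the laboratory outcomes, so there is no stated figure to reproduce. The check asks how far unequal testing alone could move the rates.

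**Inputs from the documents**
- 35 subjects per arm (6.4).
- A four-calendar-day window (5.4).
- Potassium and total calcium at least every 12 hours in PICU patients with active shock (4.6.1). Over four days this is 96/12 = 8 tests, used as the reference count.

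**Assumed inputs**
- The same per-test risk in both arms.
- A 10% event rate at 8 tests.
- The other arm tested 1.25, 1.5 or 2 times as often (10, 12 or 16 tests).
- Within-patient correlation between tests of 0 or 0.3.

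**Independent tests.** P(event) = 1 − (1 − p)^k. Setting this to 0.10 at k = 8 gives p = 1 − 0.9^(1/8) = 0.0131. Then:
- k = 10: 1 − 0.9^1.25 = 12.3%
- k = 12: 1 − 0.9^1.5 = 14.6%
- k = 16: 1 − 0.9^2 = 19.0%

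**Correlated tests.** With a beta-binomial model, P(event) = 1 − B(a, b + k)/B(a, b), where a + b = (1 − ρ)/ρ and the mean is chosen to give 10% at k = 8. For ρ = 0.3, a + b = 2.33, and the fit gives a = 0.063 and b = 2.271.

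| Testing ratio | Independent | ρ = 0.3 |
|---|---|---|
| 1.0 | 10.0% | 10.0% |
| 1.25 | 12.3% | 11.0% |
| 1.5 | 14.6% | 11.9% |
| 2.0 | 19.0% | 13.3% |

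From a 40% reference rate, 1.5 times the testing gives 53.5% (independent) or 45.8% (ρ = 0.3).

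**In the pilot.** At a ratio of 1.5 with independent tests, expected events are 35 × 0.10 = 3.5 against 35 × 0.146 = 5.1. By exact binomial calculation the more-tested arm shows more events in 66% of trials, the same number in 12% and fewer in 22%. With equal testing a named arm shows more in 42%. With ρ = 0.3 the expected counts are 3.5 against 35 × 0.119 = 4.2.

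**In a later trial.** With an assumed 1,000 per arm and a two-sided 5% test of two proportions, a ratio of 1.5 would give a false significant difference in 88% of trials (independent) or 28% (ρ = 0.3).

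**The repeat-test wording.** For potassium the stopping criterion is "Hyperkalemia defined as blood potassium >6 mEq/L confirmed on immediate repeat testing". Its limit equals the endpoint limit, so a subject with a non-hemolyzed sample is already an event and the repeat cannot add one. For ionized calcium the criterion is "ionized calcium >0.35 mmol/L confirmed on immediate repeat testing". The endpoint in 5.4 is 1.35 mEq/L, and calcium is divalent, so that is 1.35/2 = 0.675 mmol/L. The stopping limit as written is below the endpoint, so an LR-only repeat could add looks. That depends on figures that disagree:
- Ionized calcium is 1.35 mmol/L in 3.4.2, 0.35 mmol/L in 4.6.1 and 1.35 mEq/L in 5.4.
- Total calcium is 12 mg/dL in 3.4.2 and 4.6.1 but 12 mEq/L in 5.4, and 12 × 40.078/2/10 = 24.0 mg/dL.

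**The case against.** The strongest answer is that unequal testing is a conjecture. The PICU pathway frequencies in 4.6.1 do not depend on arm, and continuing resuscitation outside the ED is expected almost entirely in the PICU. Section 3.4.2 says that potassium, calcium and liver tests are measured in all patients with suspected septic shock. Section 6.3.4 describes routine testing as daily or more frequent. Discretionary stopping for electrolyte concerns in 3.1.2 is not confined to LR. The LR-only list directly touches two of the six outcomes, since ALT and bilirubin are not 5.4 outcomes. The pilot is not powered for safety and plans no formal comparison. Relying on routine care is a deliberate choice, argued in 5.1.2.

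Most of this stands. It makes a large imbalance less likely, but it does not measure it. The pathway frequencies cover PICU patients with active shock, and 4.6.1 says that the hospital has no corresponding guideline for patients admitted to the floor after shock resolves.

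A reader might infer several stronger things that the documents do not support:
- **That the LR arm will be tested more, or will show more toxicity.** No section shows unequal testing, and the effect is a tendency on average, not a certainty at 35 per arm.
- **That untested subjects are counted as event-free, or that availability will be reported only overall.** Sections 5.4 and 6.3.4 are silent on both.
- **That doubling the tests nearly doubles the rate.** This needs independent tests as well as a twofold ratio. With ρ = 0.3 the rate goes from 10% to 13.3%.
- **That the repeat rule inflates hyperkalemia.** It applies only once the endpoint limit has been passed.

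**Conclusion.** The point holds as a conditional one. The outcome definition, discretionary open-label testing and LR-only potassium and calcium criteria together mean that unequal testing would bias the by-arm laboratory rates, and 6.3.4 commits to nothing that would show whether testing was unequal. At 1.5 times the testing, a 10% rate would read as 11.9% to 14.6%, depending on whether the within-patient correlation is 0.3 or 0. The 10% rate, the testing ratios and the correlation are assumptions; only the 12-hourly frequency behind the 8 tests comes from the protocol. In the pilot this is about one or two extra events and affects a descriptive table only. It would matter more if the definitions were carried unchanged into a trial of several thousand patients.

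**What to change.** Add to 6.3.4, for each analyte and by arm:

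1. The number of subjects with at least one result in the four-day window, and the distribution of tests per subject.
2. The any-abnormal-value rate among all randomized subjects, with the number untested beside it. The rate among tested subjects should be supplementary only, because being tested happens after randomization and restricting to it can introduce selection.
3. A descriptive sensitivity measure less dependent on test count, such as the first result on each calendar day of the window, with the number of subjects contributing each day.

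Separately, the ionized calcium limits and units in 3.4.2, 4.6.1 and 5.4, and the total calcium units, must be reconciled.

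The cost is a little more analysis. Section 5.1.1 already abstracts laboratory results with date and time, so no test, visit or change in care is needed. The daily-first measure can miss brief abnormalities and still depends on a test having been done that day, so it should sit beside the main rate and not replace it.
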